7.3 DATA SECURITY AND CONFIDENTIALITY

We will keep a separate password protected screening log and subject tracker on the University shared drive in a secured location. Only study personnel will have access to the electronic screening log that maps the Subject ID number and Screening ID number (if applicable) to the subject's name, medical record number (MRN) and contact information. Only limited identifiable data will be collected. All subject data recorded on paper are maintained in locked file cabinet with limited access by research staff. No one other than the research team at the University of Michigan will be given or have access to the patient's name, mailing address, email address, phone number, and other personal identifying information.

7.4 USE OF TWILIO SERVICE

We will work with the Michigan Institute for Clinical and Health Research (MICHR) to construct our REDCap database and connect it with Twilio. Twilio (<https://www.twilio.com>) is a third-party service used to send automated SMS messages and phone call surveys to users for a variety of purposes. We will use Twilio to send follow-up communications to subjects in the intervention groups on Study Days 3, 9, 9, 14, 21 and 28. The only piece of information transmitted from our REDCap database to Twilio will be the phone number of the participant. Participants will choose to either opt-in or opt-out of using Twilio service. Participants that choose to opt-in to the service must provide informed consent to use the service and must agree to Twilio's privacy policy and terms of service. All participants who refuse to use the Twilio service will be offered alternative means of follow-up including phone, text, and/or email communications directly sent from the study coordinator. No protected health information (PHI) will be requested from the patients or sent by the study team through Twilio. The only information transmitted through Twilio SMS text messages or phone calls will be non-identifiable responses to questions about the number of times per day the subject has bowel movements.

8. HUMAN SUBJECTS

8.1 INSTITUTIONAL REVIEW BOARD AND INFORMED CONSENT

This protocol, the informed consent document, and any subsequent modifications will be reviewed and approved by the Michigan Medicine IRB (IRBMED). The consent form will describe the purpose of the study, the procedures to be followed and the risks and benefits of participation. A copy of the consent form will be given to the participant, a copy uploaded to MiChart (if the subject is a Michigan Medicine patient), and the original signed consent will be stored by the coordinator in a secure location.

8.2 SUBJECT CONFIDENTIALITY

All subject evaluation forms and other records will be identified only by the Subject ID and date of completion, to maintain subject confidentiality. All records will be kept in a locked file cabinet. All computer entry will be performed using Subject ID only. Any clinical information will not be released without written permission of the subject, except as necessary for monitoring by the IRB.

8.3 POTENTIAL RISKS AND BENEFITS

There is minimal medical risk to any participant in this study. Patients will be counselled on the risk of cirrhosis complications (ascites, HE) that may be related to their underlying disease as well as side effects associated with lactulose: abdominal discomfort, bloating, diarrhea, dehydration and rarely hypernatremia and/or hypokalemia. Participants can withdrawal at any time. The potential benefits to participants include an improvement in HRQOL, cognitive function and overall sleep quality and reduction in the risk of developing HE.

The known or expected risks are:

- **Questionnaires:** Many of the questions relate to how the subjects are feeling, and this may lead to an emotional reaction. To minimize these risks, questions will not ask explicitly sensitive information and study coordinators will be available for support. Additionally, should the questionnaires or surveys become uncomfortable, subjects can choose to skip any question that they do not wish to answer or stop at any time.
- **Loss of confidentiality:** There is rare risk of loss of confidentiality or privacy. To reduce the risk of loss of confidentiality, trained members of the research team will ask subjects questions in a private patient room. This information will be limited to the subject's name, date of birth, sex, and subject ID. Information such as the subject's full name and phone number will be recorded along with their baseline data however, this information will be stored in a locked cabinet. This data will be entered into a password-protected database where all data will be coded using a study number and only staff involved in this research will have access to the data.
- **Lactulose:** There is the possibility that that lactulose can cause physical symptoms such as abdominal pain, diarrhea, and bloating. Lactulose can rarely cause dehydration and hypernatremia (low blood sodium) and/or hypokalemia (low blood potassium).

There may be additional risks that are unknown or unexpected.

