1.2 END POINTS

All patients will be followed until death, liver transplantation or final study visit at 28 days post – enrollment.

Primary Endpoint

1. Comparison of SF-8 at 28 days post-baseline, between the two groups.

Secondary Endpoints

1. Comparison of ANT, overall sleep quality, regular daily activity impairment, falls, and average number of daily bowel movements at 28 days, compared between the two groups.

[figure not shown]

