6. STATISTICAL CONSIDERATIONS

6.1 SAMPLE SIZE AND ACCRUAL

While no studies of lactulose enrolling patients exclusively with deficits in quality of life, one high quality study of lactulose therapy have been performed for patients with cognitive dysfunction defined by psychometric testing. Lactulose was associated with a 6.81 95%CI (5.2-8.4) point or 65% relative improvement in health-related quality of life using the Sickness Impact Profile compared to control. Given this magnitude of effect, very few patients need to be enrolled. However, if we hypothesize an attenuated effect (30% improvement), seeking to enroll with a 1:1 randomization, assuming an alpha of 0.05, we will have 90% power to detect a difference among 42 subjects. We will therefore proceed with a study of 50 patients to allow for additional adjustment of baseline covariates and drop-outs.

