6.2 QUANTITATIVE ANALYSIS

We will compare differences in all outcomes, each continuous variable, using MANOVA. Multiple linear regression will be used to adjust for baseline covariates.

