18.1 If yes, number of falls: _____

4. What is the current average number of bowel movements you have per day? _____

5. During the past seven days, how much did your CIRRHOSIS affect your ability to do your regular daily activities, other than work at a job?

By regular activities we mean the usual activities you do, such as work around the house, shopping, childcare, exercising, studying, etc. Think about times you were limited in the amount or kind of activities you could do and times you accomplished less than you would like. If CIRRHOSIS affected your daily activities only a little, choose a low number. Choose a high number if CIRRHOSIS affected your activities a great deal.

CIRRHOSIS had no effect on my work

CIRRHOSIS completely prevented me from working

0 1 2 3 4 5 6 7 8 9 10

CIRCLE A NUMBER

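### A joint MANOVA on six outcomes can drop a subject whose SF-8 was collected because another outcome is blank

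*Combined protocol and SAP*

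**What the plan says.** The whole analysis plan is two sentences in section 6.2: "We will compare differences in all outcomes, each continuous variable, using MANOVA", and "Multiple linear regression will be used to adjust for baseline covariates". The outcome and covariates of the regression are not named, nor is its rank against the MANOVA.

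Section 1.2 gives one primary endpoint, "Comparison of SF-8 at 28 days post-baseline, between the two groups". The secondary endpoints add five more outcomes: "Comparison of ANT, overall sleep quality, regular daily activity impairment, falls, and average number of daily bowel movements at 28 days". That makes six.

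On incomplete data, section 8.3 tells subjects who find the questionnaires uncomfortable that they may leave items blank: "subjects can choose to skip any question that they do not wish to answer or stop at any time". Section 4.4 holds the day-28 visit by REDCap email and/or phone, whereas the ANT in Appendix D is timed by staff with a stopwatch. In Appendix G the falls count ("If yes, number of falls") is requested only after a 'Yes'. Section 5.1.2 lists uncollected outcome assessments as a protocol deviation but does not say how they are analysed. The protocol has no analysis set, imputation method or missing-item rule.

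Section 6.1 sets the size: "assuming an alpha of 0.05, we will have 90% power to detect a difference among 42 subjects". It then rounds up to 50 for covariate adjustment and drop-outs. Section 2 allows enrolment of up to 75 so that 50 complete.

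**The concern.** MANOVA treats the outcomes as one response vector, and a standard fit discards any subject with a gap in it. Under section 6.2 as written, a skipped sleep, activity, falls or bowel-movement item, or an ANT that was never administered, can take a subject out of the comparison even though the SF-8 is on file. The ANT route is realistic: a subject can return the emailed forms and never be reached by phone.

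At stake is the loss of randomized subjects with an observed primary outcome, for reasons that need not concern that outcome, in a trial planned around 50. The allowances in sections 6.1 and 2 name losses of whole subjects and covariate adjustment. Neither mentions skipped items, and nothing says that a completer with a partial record is replaced.

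**Working it through.** **The plan's own figure.** The 42 in section 6.1 cannot be reproduced, because no SD and no SF-8 point difference are given. It can only be back-solved. With 21 per arm, 90% power and two-sided alpha 0.05 (sidedness is not stated), the normal approximation gives a standardized difference of √(2/21) × (1.960 + 1.282) = 1.00. That value is used below only to put power beside the counts.

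**Inputs.** Six outcomes (section 1.2). 50 completers (sections 2 and 6.1). A per-outcome missing rate m, which is not in the documents and is assumed to be 1%, 2%, 3% or 5%.

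**Mechanism.** In 50 simulated subjects, one falls value, one ANT value and one bowel-movement value were blanked in three different subjects. The six-outcome MANOVA used 47 rows. A linear regression on SF-8 alone used all 50.

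**Counts.** Two patterns of missingness bracket the plausible cases:

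- Independent: all six outcomes go missing separately, so complete vectors = 50 × (1 − m)^6.
- Clustered: sleep, falls, bowel movements and activity impairment are all on the Appendix G form. If they go missing together, there are three units (SF-8, ANT, form), so complete vectors = 50 × (1 − m)^3.

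SF-8 alone keeps 50 × (1 − m).

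| m (assumed) | Independent | Clustered | SF-8 alone | SF-8 present but lost: independent / clustered |
|---|---|---|---|---|
| 1% | 47.1 | 48.5 | 49.5 | 2.4 / 1.0 |
| 2% | 44.3 | 47.1 | 49.0 | 4.7 / 1.9 |
| 3% | 41.6 | 45.6 | 48.5 | 6.9 / 2.9 |
| 5% | 36.8 | 42.9 | 47.5 | 10.7 / 4.6 |

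**Break-even.** The rate that takes 50 down to 42 is 1 − (42/50)^(1/6) = 2.9% if independent, and 1 − (42/50)^(1/3) = 5.7% if clustered.

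**Power.** For a two-group SF-8 comparison in the retained subjects, power = Φ(1.00 × √(N/4) − 1.96):

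- N = 50: 94%.
- m = 3%, independent (41.6): 90%.
- m = 5%, independent (36.8): 86%.
- m = 5%, clustered (42.9): 91%.
- m = 5%, SF-8 alone (47.5): 93%.

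These figures show the effect of losing subjects. They are not the power of the joint MANOVA test.

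**Falls.** A subject who answers 'No' has an empty count field by design. Unless that is coded as zero, a standard fit drops every subject who did not fall. The documents give no proportion, so this is not in the table.

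**The case against.** The best answer is that deletion is nowhere stated. It is the default behaviour of the method, and section 6.2 also plans a regression. Sections 1.1.1 and 1.2 define the primary comparison on SF-8 alone, so a regression on SF-8 would keep these subjects, subject to complete covariates. That is true, but the plan does not say that SF-8 is the regression outcome or that the regression is primary. The choice remains open until the data are seen.

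Item non-response may also be low. Skipping is offered for discomfort, section 8.3 says the questions avoid explicitly sensitive matters, Appendix C asks for every item to be answered, and section 4.9 pays for completing all activities. The ANT is a test rather than a question, so a blank there would come from stopping or from non-collection. All of this stands and is why the 1% row belongs in the table.

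The table counts SF-8 as one outcome, although it has one item per domain. If 3% were a rate per item, all eight would be complete in only 50 × 0.97^8 = 39.2, and analysing SF-8 alone would not recover those subjects. The gain shown therefore applies to subjects whose SF-8 can be scored.

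A reader might infer that lactulose subjects are lost more often because they face intrusive stool questions. The documents do not support that. Section 4.4 gives the follow-up questionnaire, with its bowel-movement item, to every subject, and section 4.3.2 collects stool data from all. The Summary and section 7.4 describe the automated messages as going to the treatment arm, but the day-28 question is the same in both. Side effects in an unblinded arm could still make the loss unequal. That is possible, not shown.

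**Conclusion.** The concern holds in a limited form. As written, section 6.2 permits an analysis in which a blank secondary or exploratory outcome removes a subject with an observed primary outcome, and no rule in the protocol prevents it. At assumed rates of 1% to 5% per outcome, between about 1 and 11 of 50 subjects with SF-8 in hand would be lost. The result depends on a rate that the documents do not give and on how far blanks cluster within subjects.

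A reader might go further and conclude that item non-response consumes the 42-to-50 margin before any drop-out. The figures do not establish that. Only independent missingness at about 3% or more goes below 42, while the clustered pattern stays above 42 through 5%. Whole-subject losses are also covered by enrolment of up to 75, so they need not come out of the 50. The supportable statement is that the margin is eroded. The change is still worth making, because it removes the loss at almost no cost.

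**What to change.** In section 6.2:

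1. Name as the primary analysis a baseline-adjusted linear regression on day-28 SF-8, in every randomized subject with that outcome, whatever else is missing.
2. Analyse each other outcome separately in all subjects who have it.
3. Impute missing baseline covariates rather than exclude the subject. Otherwise a skipped baseline item brings the same loss back.
4. Code a 'No' to falls as zero.
5. State how a partly completed SF-8 is scored, since the plan has no rule for it.

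Optionally, add a one-time REDCap prompt when an SF-8 item is left blank, with a 'prefer not to answer' choice. The right to skip is kept.

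The cost is a few sentences and a field setting, through an IRB-approved amendment as section 8.4 requires. The downside is that denominators differ slightly between outcomes, so each table should report its own.

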Appendix A. Demographics Questionnaire**Mi-Kristal Trial Demographics Questionnaire**

Instructions: Please answer the following demographics questions. Please note that your answers will be kept completely confidential. Please record the date the form was completed on the top of this page.

1. What is your age in years?

Age: _____

2. What is your sex?

Male
 Female
 Other (please state): _____

3. What is your ethnicity?

Hispanic or Latino
 Not Hispanic or Latino
 Unknown
 Not Reported

4. What is your race? (select all that apply)

 American Indian or Alaska Native	 White
 Asian	 Unknown
 Black or African-American	 Not Reported
 Native Hawaiian or Other Pacific Islander	

5. What is the highest education level that you have completed?

 No schooling completed	 Nursery school to 8 th grade
 Some high school, no diploma	 High school graduate
 GED or equivalent	 Some college, no degree
 Associate degree: occupational, technical, or vocational program	
 Associate degree: academic program	
 Bachelor's degree (e.g., BA, AB, BS, BBA)	
 Master's degree (e.g., MA, MS, MPH, MEng, MEd, MBA)	
 Professional school degree (e.g., MD, DDS, DVM, JD)	
 Doctoral degree (e.g., PhD)	 Unknown

6. What is your marital/partner status?

Never Married/Single Separated

Married Divorced Domestic Partnership Widowed

7. What is your current employment status?

 Employed full-time Employed part-time Retired On disability Not employed

8. What is your annual income?

 Less than \$10,000 \$75,000 to \$99,999 \$10,000 to \$14,999 \$100,000 to \$149,999 \$15,000 to \$24,999 \$150,000 to \$199,999 \$25,000 to \$34, 999 \$200,000 or more \$35,000 to \$49,999 Unknown \$50,000 to \$74,999

9. What type of geographic area do you live in?

 Rural Suburban Urban

Appendix B. Health History Questionnaire**Mi-Kristal Trial Health History Questionnaire**

Instructions: Please answer the following questions about your health history to the best of your knowledge. Please record the date the form was completed on the top of this page.

1. What is the underlying cause of your cirrhosis? (check all that apply)

 Alcohol	 Nonalcoholic fatty liver disease (NAFLD)
 Hepatitis C	 Primary biliary cirrhosis (PBC)
 Hepatitis B	 Primary sclerosing cholangitis (PSC)
 Autoimmune Hepatitis	 Other (please specify): _____

2. Do you currently have liver cancer?

 Yes
 No
 Unknown

a. If "No" or "Unknown," do you have any history of liver cancer?

 Yes
 No
 Unknown

3. Are you on the liver transplant waiting list?

 Yes
 No
 Currently undergoing transplant evaluation
 Recently removed from the transplant waiting list

4.1 If recently removed, how long ago was removal (in months): _____

4.2 If recently removed, specify reason for removal: _____

4. Have you stopped driving within the past 6 months?

 Yes	 Stopped driving more than 6 months ago
 No	

5. Are you dependent upon assistance from anyone for any of the following (check all that apply)?

 Bathing	 Getting out of bed or chair
 Dressing	 Eating
 Using the toilet/going to the bathroom	 None

6. Have you been hospitalized in the past 90 days?

No
 Yes

6.1 If yes, number of hospitalizations: 1 2 3 More than 3

7. Have you had an Emergency Room (ER) visit in the past 90 days?

No
 Yes

7.1 If yes, number of ER visits: 1 2 3 More than 3

8. Do you have ascites (accumulation of fluid in the abdomen)?

Yes
 No
 Unknown

9. Do you currently take diuretics/water pills (e.g. Lasix/Furosemide, Aldactone/Spironolactone)?

Yes
 No
 Unknown

10. Have you had a paracentesis (a procedure to remove fluid from the abdomen) within the last 90 days?

Yes
 No
 Unknown

11. Have you have a Transjugular intrahepatic portosystemic shunt (TIPS)?

Yes
 No
 Unknown

12. Are you currently receiving dialysis?

Yes
 No
 Unknown

13. Do you have diabetes?

Yes
 No
 Unknown

14. Do you have congestive heart failure (CHF)?

- Yes
- No
- Unknown

15. Do you have chronic obstructive pulmonary disease (COPD)?

- Yes
- No
- Unknown

16. During the past month, how would you rate your sleep quality overall?

- Very Good
- Fairly Good
- Fairly Bad
- Very Bad

17. Have you had any falls in the past 4 weeks?

- Yes
- No

17.1 If yes, number of falls: _____

18. What is the current (past 2 weeks) average number of bowel movements you have per day?

Appendix C. SF-8

Mi-Kristal Trial SF-8 Health Survey

Instructions: This survey asks for your views about your health. This information will help you keep track of how you feel and how well you are able to do your usual activities. Answer every question by selecting the answer as indicated. If you are unsure about how to answer a question, please give the best answer you can. For each of the following questions, please mark an [x] in the one box that best describes your answer. Please note that your answers will be kept completely confidential. Please record the date the form was completed on the top of this page.

3. Overall, how would you rate your health during the **past 4 weeks**?

Excellent Very good Good Fair Poor Very poor

4. During the **past 4 weeks**, how much did physical health problems limit your usual physical activities (such as walking or climbing stairs)?

None at all Very little Somewhat Quite a lot Could not do physical activities

5. During the **past 4 weeks**, how much difficulty did you have doing your daily work, both at home and away from home, because of your physical health?

None at all A little bit Some Quite a lot Could not do daily work

6. How much bodily pain have you had during the **past 4 weeks**?

None Very mild Mild Moderate Severe Very Severe

7. During the **past 4 weeks**, how much energy did you have?

Very much Quite a lot Some A little None

8. During the **past 4 weeks**, how much did your physical health or emotional problems limit your usual social activities with family or friends?

None at all Very little Somewhat Quite a lot Could not do social activities

9. During the **past 4 weeks**, how much have you been bothered by emotional problems (such as feeling anxious, depressed or irritable)?

None at all Slightly Moderately Quite a lot Extremely

10. During the **past 4 weeks**, how much did personal or emotional problems keep you from doing your usual work, school or other daily activities?

None at all Very little Somewhat Quite a lot Could not do daily activities

Appendix D. ANT

Mi-Kristal Trial Animal Naming Test

Instructions: Instruct the subject to recall and name as many animals as possible and track the subject's performance for 60-seconds. Set your stopwatch and tell the subject to start when you say GO. Tell the subject to STOP when the stopwatch reads 60-seconds. Keep track of the number of animals they say with the space provided below. When the test is done add your tally marks and indicate the total in the box below. The score is the number of correctly produced animal names during the 60-seconds. Please record the date the form was completed on the top of this page.

Use this space to keep tally of the number of correctly pronounced animal names

SCORE (The sum of all correctly produced animal names)

Appendix E. AUDIT-C**Mi-Kristal Trial AUDIT-C Questionnaire**

Instructions: Please answer the following questions related to alcohol use to the best of your knowledge. Please note that your answers will be kept completely confidential. Please record the date the form was completed on the top of this page.

1. How often did you have a drink containing alcohol in the past year?
 Never
 Monthly or less
 2-4 times per month
 2-3 times per week
 4 or more times a week
2. How many drinks containing alcohol did you have on a typical day when you were drinking in the past year?
 1 or 2 drinks
 3 or 4 drinks
 5 or 6 drinks
 7 to 9 drinks
 10 or more drinks
3. How often did you have six or more drinks on one occasion in the past year?
 Never
 Less than monthly
 Monthly
 Weekly
 Daily or almost daily

Appendix F. Final Screening Questions**Mi-Kristal Trial Final Screening Questions**

Instructions: Below are the final screening questions for potential subjects. Ask potential subjects these questions prior to consent to confirm eligibility. Please record the patient's Screening ID and the date the form was completed on the top of this page. If the patient is enrolled as a subject, this document should be retained in their study chart.

1. Have you ever had a liver transplant? (patient must answer **NO** to be eligible)

Yes
 No

2. Have you ever taken lactulose? (patient must answer **NO** to be eligible)

Yes
 No

3. Have you been told by doctor that you have hepatic encephalopathy (HE) within the past 6 months? (patient must answer **NO** to be eligible)

Yes
 No

4. Are you currently eating a low galactose diet? (patient must answer **NO** to be eligible)

Yes
 No

5. During the past seven days, how much did your CIRRHOSIS affect your ability to do your regular daily activities, other than work at a job? (patient must answer **≥ 3** to be eligible)

By regular activities we mean the usual activities you do, such as work around the house, shopping, childcare, exercising, studying, etc. Think about times you were limited in the amount or kind of activities you could do and times you accomplished less than you would like. If CIRRHOSIS affected your daily activities only a little, choose a low number. Choose a high number if CIRRHOSIS affected your activities a great deal.

CIRRHOSIS had no effect on my work

CIRRHOSIS completely prevented me from working

0 1 2 3 4 5 6 7 8 9 10

CIRCLE A NUMBER

6. Based on preliminary screening and these responses, is the patient eligible to participate in this study?

- Yes, they are eligible, and they have been enrolled. Their subject ID is _____.
- Yes, they are eligible, but they have not been enrolled because _____.
- No, they are not eligible because _____.

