3. SELECTION AND ENROLLMENT OF SUBJECTS

3.1 INCLUSION CRITERIA

All subjects must meet the following criteria:

1. *Adult ≥ 18 years of age*
2. *Diagnosis of cirrhosis – must meet one of the following criteria:*
 - a. *liver biopsy, OR*
 - b. *history of cirrhosis complication: ascites, variceal bleeding, hepatic encephalopathy, OR*
 - c. *2 of the following 4 criteria:*
 1. *US, CT or MRI imaging findings of cirrhosis (cirrhotic appearing liver, splenomegaly, varices, ascites)*
 2. *Fibroscan liver stiffness score >13 kPa*
 3. *Laboratory testing: AST/platelet ratio index (APRI) >2.0*
 4. *CT, MRI or EGD showing presence of esophageal varices*
3. *Evidence of portal hypertension – must meet at least one of the following criteria:*
 - a. *Ascites*
 - b. *Varices (seen by endoscopy or by ultrasound or cross-sectional imaging)*
 - c. *Fibroscan liver stiffness measurement (LSM) > 25*
 - d. *Platelets < 80*
4. *Moderate activity impairment*
 - a. *≥ 3 on WPAI regular daily activity impairment question (scored 0-10)*

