4.2.2 Randomization

After informed consent and baseline procedures are completed, the study coordinator will randomize the subject via reandomize.net. Subjects will be randomized in approximately equal allocation to each arm 1:1 lactulose therapy or the control group. Randomization is stratified by subject self-reported activity impairment level. Activity impairment level is determined by the baseline WPAI regular daily activity impairment score collected as part of the final screening questions (Appendix F): mild/moderate is a score of ≤ 7 , severe is a score of > 7 . To ensure approximate balance within arms, the randomization will be implemented using a randomly permuted blocks design to ensure approximate balanced assignments within subject self-reported

activity impairment severity level. The sequence of assignments for each stratum will be prepared in advance by a biostatistician.

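### The activity-impairment item asks about daily activities outside a job, but both ends of its 0-10 scale are worded for work, and the score sets eligibility, stratum and the Aim 4 outcome

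*Combined protocol and SAP*

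**What the plan says.** Appendix F item 5, put to patients before consent, asks "how much did your CIRRHOSIS affect your ability to do your regular daily activities, other than work at a job". It then explains the term: "By regular activities we mean the usual activities you do, such as work around the house, shopping, childcare, exercising, studying, etc". A scoring instruction follows, telling the respondent to pick a low number if daily activities were little affected and a high number if they were greatly affected. The only two labelled points on the scale are 0, "CIRRHOSIS had no effect on my work", and 10, "CIRRHOSIS completely prevented me from working". Appendix G item 5, used at Day 28, repeats the stem, explanation, instruction and both anchors.

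The score has these uses:

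- **Entry.** Section 3.1, criterion 4, and Appendix F require at least 3.
- **Stratification.** Section 4.2.2 states "Randomization is stratified by subject self-reported activity impairment level" and "Activity impairment level is determined by the baseline WPAI regular daily activity impairment score", taken from Appendix F. The strata are scores up to 7 and scores above 7.
- **Outcome.** Aim 4 (Section 1.1.3, exploratory) compares the score from baseline to 28 days between arms. Section 1.2 lists the same measure under the secondary endpoints.

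**The concern.** The stem sets employment aside, and the anchors then bring in a word that many people will take to mean employment. Appendix A, item 7, provides for subjects who are retired, on disability or not employed. For them the two readings can give very different answers. A retired person can truthfully say that cirrhosis had no effect on work, and a person on disability can truthfully say that it prevented work altogether. In both cases daily activity may lie anywhere on the scale.

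The item carries more weight than a single exploratory question usually does. The Significance section rests the trial on a one-question 0-10 rating of how far cirrhosis affects daily activity, which is said to separate patients at low and high risk of hepatic encephalopathy. If the item measures something else in some respondents, the enrolled population departs from the one intended, and a listed endpoint loses precision.

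**Working it through.** The plan gives no figure on this point to reproduce, so the check compares the texts and traces each use of the score.

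**Step 1: stem against anchors (Appendices F and G, item 5).**

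| Part of item | What it refers to |
|---|---|
| Stem | Regular daily activities, with job work excluded |
| Explanation | Housework, shopping, childcare, exercise, study |
| Scoring instruction | Daily activities |
| Anchor at 0 | Work |
| Anchor at 10 | Working |

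Three parts agree with each other and both anchors differ from them. The mismatch is the same in the two appendices, which makes a text-extraction fault unlikely.

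**Step 2: is there another baseline value?** Neither the Health History Questionnaire contents in Section 4.1.1 nor the form in Appendix B contains an activity-impairment item. The Appendix F screening answer is therefore the only baseline for Aim 4.

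**Step 3: what a job-based answer does at each use.** With entry at 3 or more on a whole-number scale, the strata are in effect 3 to 7 and 8 to 10.

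- *Job-based answer of 0 to 2 at screening, true activity impairment 3 or more.* The person is wrongly excluded. That person never reaches Aim 4, so this route costs recruits and alters the population but does not dilute the outcome.
- *Job-based answer of 3 or more, true activity impairment below 3.* The person is wrongly included.
- *Job-based answer of 8 to 10, true activity impairment 3 to 7.* The person is eligible but in the wrong stratum.
- *Job-based answers at both screening and Day 28.* A subject who answers 10 both times because employment is out of reach shows no change, whatever happened to daily activity. This makes Aim 4 less sensitive.
- *Different readings at the two times.* The within-subject change then mixes two constructs. This is possible because staff ask the screening question, whereas Section 4.4 allows Day 28 by REDCap email and/or phone, so some subjects may read the anchors unaided.

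**Step 4: what is untouched.** The wording is the same in both arms, so by itself it does not favour either. Permuted blocks within a noisy stratum still randomize validly. The SF-8 (Appendix C) is a separate instrument. The sample size in Section 6.1 rests on a quality-of-life effect and does not use this item.

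**The case against.** The strongest defence is that a respondent must pass over the stem, the explanation and the scoring instruction to answer about a job. The explanation puts housework first among its examples, so the word in the anchors can be read as falling within the stem. At screening a staff member asks the question and can query an odd answer. All of this stands and makes misreading less likely. It does not remove the conflict, because the anchors are the only labels on the scale itself, and the staff safeguard is weaker at Day 28.

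Rewording also carries a risk. The documents do not show which anchors the one-question scale cited in the Significance section used. If they were worded for work, a change would loosen the link to that scale; if they were worded for activities, it would restore the link. This stands, and it is a reason to check before editing.

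A reader might go further and infer a stated percentage loss of effect in Aim 4, or a corresponding increase in the number of subjects needed. The documents do not support either. They give no misreading rate, and any such figure would also have to assume that job-based answers show no treatment effect and that the variance is unchanged. Nor can the rate be inferred from age: the Significance section says that two-thirds of contemporary patients with cirrhosis are at least 60, but gives no employment figure and does not describe this trial's sample.

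**Conclusion.** The stem-anchor mismatch is certain from the text and is present at both time points. It is more than a slip of style, because the form as written can misclassify people at the cut-offs of 3 and 7 and add error to a listed endpoint. Its size is unknown and cannot be derived from the documents. The consequences rest on one assumption: that some respondents follow the anchors rather than the stem and instructions.

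A reader might infer that the treatment comparison is biased or that the primary result is compromised. Neither follows. The wording is identical across arms, and measurement of the SF-8 does not depend on this item. The point should be corrected, but it does not threaten the primary endpoint.

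**What to change.** First, check the anchors of the one-question scale on which the Significance section relies. Then, in both Appendix F item 5 and Appendix G item 5, reword the anchors to match the stem: at 0, no effect on my regular daily activities; at 10, completely prevented me from doing my regular daily activities. If this departs from the source scale, the protocol should say so.

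If enrolment has begun, record the wording version with each score and give each subject the same version at screening and at Day 28. A change date alone is not enough, because a subject screened on one version and followed up on the other would have a change score that is not comparable.

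The cost is an edit to two forms and a written amendment approved by the IRB, as Section 8.4 requires. If the change is made mid-trial, the data will also hold two wording versions.
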